#### 5.1 Data Analysis plan

The primary analysis is to estimate the prevalence of SCD-related vision loss. In addition to the calculated value, a corresponding 95% confidence interval will be obtained to illustrate its associated uncertainty. We will also calculate prevalence of each stage of SCR and maculopathy by age bracket and genotype. The unit of analysis will be the eye with the worse SCR stage, or randomly chosen eye if both are of the same stage. The chi-square test for trend will be used if groups are ordinal. The Kruskal-Wallis test (categorical factors) or Spearman rank (ordinal factors) will be used when comparing SCR stage between groups, as above.

The association between SCD severity (as assessed by number of hospital admissions in past year and haemoglobin and haemoglobin F level within 3 months) with SCR stage and presence of sickle maculopathy will be examined using Spearman Rank or Pearson product correlation. Multivariable analysis such as logistic regression will be undertaken to assess the simultaneous effects of multiple factors on stage of SCR and presence of maculopathy. The correlation between NEI VFQ-25 global score and acceptability with best

corrected visual acuity, SCR stage and presence of maculopathy will also be assessed using Spearman rank correlation.

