# 1. Introduction

# 1.1 Proliferative sickle cell retinopathy

Sickle-cell disease (SCD) is one of the most common genetic disorders in the UK, with approximately 15000 people affected. It is a debilitating, multisystem disease, associated with episodes of acute illness, progressive organ damage and reduced life expectancy. There are 13 genetic variants of SCD, with HbSS genotype being most common (>70%) and most severe, followed by HbSC genotype. SCD affects predominantly people of African and Afro-Caribbean descent and evidence demonstrates inequalities in healthcare outcomes and access for people with SCD . An all-party parliamentary group inquiry reported low awareness of SCD and its complications among healthcare professionals and underinvestment in sickle cell research.

Proliferative sickle cell retinopathy (SCR) is the most common ophthalmic manifestation of SCD and can result in significant sight loss, although the prevalence in the U.K is not currently known. Decades old retrospective and cohort studies from other countries have estimated prevalence of SCR in SCD patients at up to 48% and associated with significant sight loss in up to 12%. Importantly, life expectancy for SCD has increased from 14 years in 1973 to >60 years in high-income countries with improvement in management and healthcare delivery. Evidence from cohort studies and large retrospective studies demonstrate increasing incidence of SCR with age. As such, we could expect the prevalence of SCR and potentially associated visual impairment, to be currently higher in the UK than previously reported.

Five stages of SCR were described by Goldberg in 1971. These are progressive with stages 1-3 being asymptomatic, stage 3 reflecting the presence of retinal neovascularisation in the far periphery known as seafan neovascularisation, vitreous haemorrhage (bleeding inside the eye) develops in stage 4 and rhegmatogenous and/or tractional retinal detachment in stage 5.

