#### Secondary outcomes

- 1. The prevalence of each stage of SCR and presence of maculopathy by age and genotype
- 2. The correlation of each stage of SCR and maculopathy to severity of SCD as determined by number of hospital admissions in the preceding 12 months/serum HbF/ serum Hb.
- 3. The impact of SCR and presence of maculopathy on vision-related quality of life.
- 4. The acceptability to patients of routine retinal imaging for SCR and maculopathy
- 5. The development of updated consensus definitions and a modernized classification system for SCR and maculopathy, leveraging the increased insight into retinal tissue anatomy and vascular blood flow afforded by contemporary imaging technologies

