### 5. Statistics and data analysis

The primary analysis will be to calculate the prevalence of sickle cell retinopathy/maculopthy-related vision loss together with its 95% confidence interval (CI) to illustrate the uncertainty in the estimate. It is anticipated the prevalence will be approximately 10% based on data from Saidkasimova et al. With 554 subjects the prevalence can be estimated with a 95% confidence interval with a 5% width e.g. expected to be from 7.5% to 12.5%. The sample size (N) was chosen to satisfy this 5% width, given the confidence interval is expected to be p + 1.96\*sqrt(p\*(1-p)/n), where p=0.1. To obtain this number of evaluable subjects we estimate approximately 600 subjects will have to be enrolled, this allows for a drop-out rate of just under 10%.

A sample size of 600 will also allow accurate estimates of the stages of SCR and maculopathy occurrence to be obtained. For example, the following CIs are based on a French retrospective cohort of 942 patients:

	%	N	95%CI (23%-	width
Stage 0	30%	166	37%) (34%-	14%
Stage 1-2	40%	222	46%) (13%-	13%
Stage 3	20%	110	27%)	15%
Stage 4	5%	28	(8%-20%)	12%
Stage 5	5%	28	(8%-20%)	12%
	100%	554		

Other endpoints also include the calculation of the prevalence of each stage of SCR by age bracket and genotype. Sample size relevance in these circumstances can be illustrated by considering a hypothetical outcome. For example, under the null hypothesis there would be no association between prevalence and age, and given the hypothetical distributions of stage, and age below, it can be shown that the estimated correlation (Spearman Rank) has a greater than 3 SE difference (from zero) with 554 cases. This suggests powering is adequate for associations of this size, by the 'rule of three', for 85% power (Zbeta=1) and 5% sig level (Zalpha=1.96).

				Age Group					
				O. Guip					rate
N		3.1%	7.4%	8.2%	14.0%	16.9%	21.7%	9.7%	overall
	Stage/Age	16-25	 26-35	36-45	46-55	56-65	66+		
	5	1	5	6	6	5	2		
SCR	4	2	5	5	8	6	3		
	3	23	28	28	20	12	4		
	1-2	46	56	55	39	23	8		
	0	24	42	40	27	19	6		
	l	96	136	134	100	65	23	554	
		Spearm	an Rank -	0.14 (95%	CI:-0.23 t	o -0.06), p	o=0.001		

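### Section 5.1 names rank tests over all SCR stages but no test of stage 4 or worse, the one rate that the planning table shows rising clearly with age

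*Protocol*

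**What the plan says.** The first secondary outcome in Protocol section 2.1 is "The prevalence of each stage of SCR and presence of maculopathy by age and genotype". Section 5 repeats it ("Other endpoints also include the calculation of the prevalence of each stage of SCR by age bracket and genotype") and section 5.1 plans it: "We will also calculate prevalence of each stage of SCR and maculopathy by age bracket and genotype".

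For testing, section 5.1 says "The chi-square test for trend will be used if groups are ordinal", without naming the outcome contrast. It assigns Kruskal-Wallis to categorical factors, and "Spearman rank (ordinal factors) will be used when comparing SCR stage between groups, as above". It adds a regression: "Multivariable analysis such as logistic regression will be undertaken to assess the simultaneous effects of multiple factors on stage of SCR". No cut-point or ordinal form is given for that model.

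Section 1.1 says of the Goldberg stages: "These are progressive with stages 1-3 being asymptomatic". It places vitreous haemorrhage at stage 4 and retinal detachment at stage 5.

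Section 5 illustrates power for the age association with a full-range Spearman correlation, "given the hypothetical distributions of stage, and age below". Above that table stands an unlabelled row of percentages: 3.1, 7.4, 8.2, 14.0, 16.9 and 21.7, with 9.7% overall.

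**The concern.** On a progressive scale, people who advance leave the lower category. The prevalence of one exclusive middle stage is therefore a balance of arrivals and departures, and need not move in the same direction as disease burden. A rank correlation over the whole scale gives most of its weight to the well-populated low stages. If the change with age sits at the top of the scale, the rank test can miss it.

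The section 5 table has this shape. It displays a roughly seven-fold rise in stage 4-5 disease (21.7/3.1 = 7.0), but the test put forward to detect the age association is the full-range rank. Section 1.5 says that the distribution of stages is wanted for planning eye services and judging screening, so the age pattern of stage 4-5 disease is a result that readers will look for.

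**Working it through.** **Inputs** (Protocol section 5, hypothetical table; ages 16-25, 26-35, 36-45, 46-55, 56-65, 66+):

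| Stage | Counts | Total |
|---|---|---|
| 5 | 1, 5, 6, 6, 5, 2 | 25 |
| 4 | 2, 5, 5, 8, 6, 3 | 29 |
| 3 | 23, 28, 28, 20, 12, 4 | 115 |
| 1-2 | 46, 56, 55, 39, 23, 8 | 227 |
| 0 | 24, 42, 40, 27, 19, 6 | 158 |
| All | 96, 136, 134, 100, 65, 23 | 554 |

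**1. The plan's own figures.** Stage 4 plus 5 by age is 3/96, 10/136, 11/134, 14/100, 11/65, 5/23 = 3.1, 7.4, 8.2, 14.0, 16.9, 21.7%. Overall it is 54/554 = 9.7%. The percentage row is reproduced exactly, so it is the stage 4-5 rate.

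The printed Spearman of -0.14 (95% CI -0.23 to -0.06, p=0.001) is not reproduced. With midranks for ties the table gives 0.060 (95% CI -0.02 to 0.14, p=0.16), about 1.4 SE from zero. The printed sign may only reflect stage 5 being listed first; the size still differs. That is a separate discrepancy. It matters here because the rank test's power has to be taken from the table.

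**2. Rank tests named in section 5.1.** Spearman power: atanh(0.0602) × √551 = 1.415, and Φ(1.415 − 1.96) = 0.29. Simulation from the table gives about 31%. Kruskal-Wallis across the six age groups gives p=0.70.

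**3. Chi-square for trend** (Cochran-Armitage, age scores x = 0 to 5):

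z = [Σcx − p̂Σnx] / √{p̂(1 − p̂)[Σnx² − (Σnx)²/N]}

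Here Σnx = 1079 and Σnx² = 3187, so the bracket is 3187 − 1079²/554 = 1085.5.

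For stage 4 or worse, Σcx = 10 + 22 + 42 + 44 + 25 = 143 and p̂ = 54/554 = 0.0975. The numerator is 143 − 0.0975 × 1079 = 37.8 (unrounded p̂). The variance is 0.0975 × 0.9025 × 1085.5 = 95.5. So z = 37.8/√95.5 = 3.87, p=0.0001. Power is Φ(3.87 − 1.96) = 0.97.

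The same formula for the other contrasts, with simulated power:

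| Contrast | % by age | z | Power |
|---|---|---|---|
| Stage 0 | 25.0, 30.9, 29.9, 27.0, 29.2, 26.1 | 0.09 | – |
| Stage 1-2 | 47.9, 41.2, 41.0, 39.0, 35.4, 34.8 | -1.67 | – |
| Stage 3 alone | 24.0, 20.6, 20.9, 20.0, 18.5, 17.4 | -0.90 | 14% |
| Stage 4 alone | 2.1, 3.7, 3.7, 8.0, 9.2, 13.0 | 2.93 | 82% |
| Stage 5 alone | 1.0, 3.7, 4.5, 6.0, 7.7, 8.7 | 2.38 | 67% |
| Stage 3 or worse | 27.1, 27.9, 29.1, 34.0, 35.4, 39.1 | 1.70 | 41% |
| Stage 4 or worse | 3.1, 7.4, 8.2, 14.0, 16.9, 21.7 | 3.87 | 97% |

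**4. Why the rank test is weak here.** Stage 0 is flat, stages 1-2 and 3 drift slightly down, and only stages 4 and 5 rise. These two hold 54 of the 554 people, so the rise is diluted in the overall ranking.

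**The case against.** The strongest reply is that the planned output already shows the pattern. Every stage is reported by age, so a reader can add stages 4 and 5. If trend tests were run on single stages, stage 4 or stage 5 would show a significant rise in about 95% of simulated studies (two unadjusted 5% tests), against 97% for the combined contrast. That stands: the signal is split, not lost.

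It is also fair that section 5.1 says stage prevalences will be calculated, and does not tie the trend test to each exclusive stage. A trend on stage 4 or worse would fit its wording, the logistic regression could use that cut-point, and an SAP not shown may fix one. The table is hypothetical, and stage 4 or worse has the largest z in it. Still, section 5.1 does name the rank tests for comparing stage, and section 5 rests its power on one of them.

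A reader might infer that the trial would report proliferative disease becoming less common with age, because stage 3 falls while stage 3 or worse rises. The documents do not support this. The fall is small, not strictly monotone and not significant (p=0.37), and the rise in stage 3 or worse also misses 5% (p=0.09). Opposite signs occur in about 76% of simulated studies, but both trends are significant in only about 0.3%. Nor are the low stages unchanged with age: stages 0-2 together go from 72.9% to 60.9%.

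**Conclusion.** The point holds as a cheap improvement, optional rather than essential, since these are secondary outcomes. With the section 5 table as truth and 554 evaluable people, the rank tests named in section 5.1 would usually miss the age pattern (Spearman power about 31%). A trend test on stage 4 or worse would usually find it (about 97%), and section 5.1 does not name that test.

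The conclusion assumes equally spaced age scores, a two-sided 5% level without multiplicity adjustment, and the hypothetical table. If real disease shifts evenly along the whole scale, the rank test would do better than shown here. The numbers support the point for age only. The protocol gives no planning figures for genotype, HbF, Hb or admissions, so extending it to them rests only on the stages being progressive. The stage 3-alone trend should be read as description.

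**What to change.** In section 5.1:

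- Keep the separate-stage prevalences as description, and say so. Do not read a trend in stage 3 alone as a trend in proliferative disease.
- Keep Spearman and Kruskal-Wallis for stage as a whole.
- Add prespecified prevalence of stage 4 or worse with a 95% CI, with a chi-square trend by age bracket and a chi-square test by genotype.
- Report stage 3 or worse alongside, noting that its power is only about 41% on the planning table.
- Label the percentage row in section 5 as the stage 4-5 rate.

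The cost is a few sentences and one or two extra secondary tests. No new data are needed.

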#### 1.2 Sickle cell maculopathy

In addition to the peripheral retina, SCD can also affect the macula (central retina) potentially causing visual loss, known as sickle cell maculopathy. Sickle cell maculopathy (SCM) is defined as patchy areas of severe retinal thinning in the temporal macula. The exact aetiology of macular thinning remains unclear, but it may be related to the temporal macula ending along the horizontal raphe, making it a watershed zone between the vascular arcades of the retinal circulation and thus more susceptible to vascular occlusions. Whilst high-contrast visual acuity was preserved in most patients demonstrated to have SCM in a single centre study, irreversible scotoma, decreased retinal sensitivity and visual loss has been described in association with SCM. Maculopathy was not included in the Goldberg classification as its presence only became more apparent with modern imaging techniques. There is currently no treatment for vision loss due to maculopathy.

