### 2.Study Objectives

The Sickle Eye Project includes an internal pilot phase, which is the first 4 months of the recruitment period, to assess recruitment and trial processes.

The objectives of the internal pilot are:

- 1. To open 6 sites by the end of the pilot phase
- 2. 95% of the expected monthly recruitment is achieved by the end of the pilot phase
- 3. Adherence to imaging protocol in ≥90% of cases
- 4. 95% of recruited participants with completed NEI VFQ 25 questionnaire

Main study primary objective: To determine the prevalence of visual impairment (best corrected visual acuity ≥LogMAR 0.3 in at least one eye) due to SCR and/or maculopathy in persons with SCD

Main study secondary objectives:

- 1. To determine the prevalence of each stage of SCR and maculopathy and correlation with:
- i) number of hospital admissions with acute sickle cell episode in the past 12 months, ii) serum HbF level iii) serum Hb level
- 2. To determine the impact of SCR and maculopathy on vision-related quality of life.
- 3.To determine the acceptability to patients of retinal imaging and routine screening for SCR and maculopathy.

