#### Main study primary outcome

1. The prevalence of visual impairment due to SCR or maculopathy (defined as best corrected visual acuity LogMAR ≥ 0.3 in at least one eye) in a representative sample of the UK population with SCD

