#### 4.Image acquisition protocol and transfer of data

Imaging acquisition will be performed by trained staff at each recruitment site. As this is a pragmatic study, and the imaging to be acquired are standard of care in NHS eye departments, standards for training and experience of staff performing the imaging acquisition function will be the ones applicable at each recruitment site as per local Standard Operating Procedures.

The Moorfields Reading Centre will provide supporting material of educational and advisory character for acquisition of high-quality imaging from the Sickle Eye Project participants. It will also provide detailed, yet simple and intuitive instructions for imaging file export and direct upload to the Moorfields Grading Portal Webbased Application.

For details on the process of User activation, including Users with the Uploader role, and User Management, please see relevant provisions of the 'Data Protection and Information Security' section.

For each patient, imaging from the three following modalities will be obtained, and transferred to the Moorfields Reading Centre. Imaging from both eyes will be obtained:

- Optical Coherence Tomography scan (TopCon 3D-2000, Heidelberg Spectralis or Zeiss Cirrus).

Recommended parameters: Macula Centre 6x6 mm Raster Scans.

- Optical Coherence Tomography Angiography where available (TopCon Triton, Heidelberg Spectralis OCT-2, Zeiss Angioplex)

Recommended parameters: Macula Centre 6x6 OCT Angiography mode

- Wide Field Imaging (Optos California or Zeiss Clarus)

Recommended parameters for wide field imaging: Instructions will be provided to assist Imaging acquisition staff with obtaining clear view of the Fundus, including the extreme periphery through imaging acquisition at the central and 4 peripheral positions of gaze (up, down, right, left) and the avoidance of 'eyelash' artifacts that interfere with Fundus view in Optos Ultra-Wide Field Imaging.

The images being transferred to Moorfield hospital will be link anonymised with no patient identifiers. The link key will remain with each recruiting site and will not be shared with the sponsor site.

Bi-directional communication between recruitment sites and the Moorfields Reading Centre will be possible through the interactive Moorfields Grading Portal. A granular Audit Log will record all study-related activity, including who, where and when each activity was performed.

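### The one-eye rule in section 5.1 suits SCR stage but not maculopathy prevalence, and it leaves open whether the person-level primary outcome is covered

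*Protocol*

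**What the plan says.** The primary outcome (Protocol section 2.1, Main study primary outcome) is visual impairment due to SCR or maculopathy, "defined as best corrected visual acuity LogMAR ≥ 0.3 in at least one eye". The primary objective in section 2 counts people: impairment "in at least one eye) due to SCR and/or maculopathy in persons with SCD". The Study summary gives the same definition.

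Section 5.1 opens with the headline estimate: "The primary analysis is to estimate the prevalence of SCD-related vision loss". After a sentence on its confidence interval it continues: "We will also calculate prevalence of each stage of SCR and maculopathy by age bracket and genotype". The next sentence is the eye rule: "The unit of analysis will be the eye with the worse SCR stage, or randomly chosen eye if both are of the same stage". The sentences after that concern the trend test and comparisons of SCR stage between groups. Section 5.1 gives no other eye rule for visual impairment, maculopathy or acuity.

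The matching secondary outcome in section 2.1 is "The prevalence of each stage of SCR and presence of maculopathy by age and genotype". Section 1.2 states: "Maculopathy was not included in the Goldberg classification". Section 4 states: "Imaging from both eyes will be obtained".

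**The concern.** The rule reduces each participant to one eye, chosen on SCR stage alone. That is sound for a variable that SCR stage itself measures. It is not sound for a condition that the staging does not record.

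Maculopathy is such a condition, and it is named in the sentence just before the rule. Under the rule, maculopathy confined to the unselected eye disappears from the count. Where both eyes have the same stage, a random draw decides whether the person counts as affected, so repeating the draw on the same data could give a different prevalence.

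A second question is whether the rule reaches the primary outcome. It has no stated limit and sits in the paragraph that opens with the primary analysis. A one-eye count is not an either-eye count, so an analyst who applied it there would estimate something other than the stated objective.

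**Working it through.** **1. The plan's own figure.** Section 5 uses p = 0.10 and a 95% interval of total width 5%. n = 1.96² × 0.10 × 0.90 / 0.025² = 553.2, rounded up to 554. The interval at n = 554 is 7.5% to 12.5%. The figure reproduces. It counts subjects, so it does not depend on the eye rule.

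**2. General relation.** Let P be the either-eye prevalence, u the share of affected people with only one eye affected, and q the chance that the selected eye is the affected one in those people.

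- One-eye prevalence = P × (1 − u + u × q)
- Share of affected people missed = u × (1 − q)

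The share missed is never negative, so the direction is certain. The documents give neither u nor q, so everything below rests on assumed values.

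**3. SCR stage.** The worse eye carries the person's stage by definition. In a tie both eyes have that stage, so the draw changes nothing. No loss.

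**4. Maculopathy.** If selection is unrelated to which eye has maculopathy, q = 0.5 and the share missed is u/2:

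| u | Share missed | An assumed 40% would read |
|---|---|---|
| 0.2 | 10% | 36% |
| 0.4 | 20% | 32% |
| 0.6 | 30% | 28% |

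The 40% is illustrative and not in the documents. In tied pairs q = 0.5 follows from the random draw. In untied pairs it is an assumption.

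**5. How often chance decides.** If the worse eye is stage 0, both eyes are stage 0 and the pair is tied. Reading the planning tables in section 5 as worse-eye stages (an assumption), stage 0 holds 166/554 = 30% in the first table and 24 + 42 + 40 + 27 + 19 + 6 = 158, or 158/554 = 28.5%, in the age table. Ties at higher stages add to this.

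A favourable case follows. Suppose 30% of one-eye maculopathy falls in tied pairs, and in untied pairs the worse-stage eye is always the affected one. Then the share missed is u × 0.30 × 0.5, which is 3% at u = 0.2 and 9% at u = 0.6.

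**6. Visual impairment, only if the rule were applied to it.** With P = 10% and 554 subjects (about 55 cases):

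| u | q | One-eye prevalence | Loss in points | Cases lost (approx.) |
|---|---|---|---|---|
| any | 1 | 10% | 0 | 0 |
| 0.5 | 0.9 | 9.5% | 0.5 | 3 |
| 0.75 | 0.9 | 9.25% | 0.75 | 4 |
| 0.5 | 0.5 | 7.5% | 2.5 | 14 |
| 0.75 | 0.5 | 6.25% | 3.75 | 21 |

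The planned half-width is 2.5 points, so the least favourable rows match or exceed it. The rows with q near 1 are negligible.

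**The case against.** A reader might infer that the rule flatly contradicts the primary outcome and biases the headline prevalence low. The documents do not support that. The either-eye definition is given in the Study summary, section 2 and section 2.1, and the study is sized in subjects. In section 5.1 the primary analysis and its interval come first, and the rule follows the move to the secondary prevalences. It can fairly be read as covering only the SCR and maculopathy analyses, and then there is no contradiction.

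The size of any loss in the primary result may also be near zero. Section 1.1 describes stages 1 to 3 as asymptomatic, with haemorrhage at stage 4 and detachment at stage 5. An eye impaired by SCR would therefore usually be the worse-stage eye and be selected. Section 1.2 reports that high-contrast acuity was preserved in most patients with maculopathy in one single-centre study, which limits the other route. These points stand, though they do not remove every route: section 1.2 also reports visual loss with maculopathy.

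On maculopathy, it can be said that no per-person definition is written down, so an undercount presumes one. That is correct. Still, the primary objective is framed in persons, and an eye-level prevalence from an eye picked on another scale has no clear interpretation.

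A reader might also infer that the rule sends the worse-stage eye's acuity into the NEI VFQ-25 correlation. Section 5.1 does not say which eye's acuity is used there, so no error is shown. Finally, using one eye per person is an accepted way to avoid within-person correlation, and the rule need not be deleted.

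**Conclusion.** For maculopathy the point holds on either reading of the rule's scope. The eye is selected on a scale that does not record the condition, one-eye disease can be missed, and in tied pairs the result depends on a draw. A per-person prevalence can only be biased low. The size cannot be obtained from the documents: 10% to 30% of affected people are missed if selection is unrelated to maculopathy and 20% to 60% have it in one eye only, and fewer if maculopathy tends to lie in the worse-stage eye.

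For the primary outcome, what stands is an unlimited rule that, read literally, conflicts with the either-eye definition. Any loss would run from near zero, if impairment comes mainly from stage 4 or 5 disease in the selected eye, to a few percentage points under less favourable assumptions. It is a scope conflict to close before analysis, not a demonstrated bias. SCR stage is not affected.

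**What to change.** Amend section 5.1 to state that:

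- visual impairment and presence of maculopathy are classified per person from both eyes, positive if either eye meets the definition;
- SCR stage per person is the stage of the worse eye, with no draw needed for ties;
- the worse-stage or random-eye rule applies only to any remaining eye-level associations.

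The cost is protocol wording. Both eyes are already imaged, and an either-eye acuity outcome already needs acuity in each eye. The 554 evaluable subjects and the expected interval of 7.5% to 12.5% do not change.
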